5.7.3.	Adverse Events of Special Interest	19
5.7.4.	Clinical Laboratory Parameters	20
5.7.5.	Vital Signs and Physical Examination	22
5.7.6.	ECG	23
5.7.7.	Columbia Suicide Severity Rating Scale (C-SSRS)	23
5.7.8.	Analysis of Data impacted by Public Health Emergency	24
5.8.	Pharmacokinetic Endpoints	24
5.8.1.	Pharmacokinetic Concentrations	24
5.8.2.	Pharmacokinetic Parameters	25
6.	Changes from Protocol-Specified Analyses	26
7.	Summary of Changes from the Previous Version of the SAP	26
8.	References	26
APPENDICES		27
Appendix A: Schedule of Activities		27
Appendix B: Study Design Schematics		30
Appendix C: Laboratory Parameters		31

LIST OF ABBREVIATIONS

ALC	absolute lymphocyte count
ALT	alanine aminotransferase
AST	aspartate aminotransferase
BL	baseline
CI	confidence interval
CRF	case report form
C-SSRS	Columbia Suicide Severity Rating Scale
DMF	dimethyl fumarate
DMT	disease-modifying therapy
DRF	diroximel fumarate
ECG	electrocardiogram
ET	early termination
EOT	end of treatment
EOS	end of study
FU	follow-up Visit
GI	gastrointestinal
HES	2-hydroxyethyl succinimide
LLN	lower limit of normal
LM	lymphocyte monitoring
MedDRA	Medical Dictionary for Regulatory Activities
MMF	monomethyl fumarate
MS	multiple sclerosis
PK	pharmacokinetic(s)
PML	progressive multifocal leukoencephalopathy
RMS	relapsing forms of MS
RNA	ribonucleic acid
RRMS	relapsing-remitting MS
SAE	serious adverse event
SAP	statistical analysis plan
TC	telephone contact
ULN	upper limit of normal

1. Introduction

This Statistical Analysis Plan (SAP) describes the statistical methods that will be used during the analysis and reporting of data collected under Biogen, MA Inc. Protocol 272MS303.

This SAP should be read in conjunction with the study protocol and electronic case report form (eCRF). This version of the SAP has been developed using Protocol Amendment 4 dated 23 May 2023 and the eCRF dated 11 August 2023.

2. Study Overview

2.1. Study Objectives and Endpoints

Table 1: Part 1 Study Objectives and Endpoints

Primary Objective	Primary Endpoints
To determine the safety and tolerability of DRF administered for up to 24 weeks in adult East Asian participants with RMS	
Incidence of AEs and SAEs at Week 24Quantitative and qualitative changes from baseline (Visit 1) to Week 24 in clinical laboratory parameters, ECGs, and vital signsIncidence of C-SSRS events at Baseline (Visit 1) and through Week 24
Secondary Objective	Secondary Endpoints
To evaluate the PK of DRF metabolites (MMF and HES) following multiple doses of DRF in a subset of adult East Asian participants with RMS	
Plasma concentrations of MMF and HESNoncompartmental plasma PK parameters of MMF and HES, including the following:
C_{max}AUC_{last}T_{max}$t_{1/2}$ (MMF only)

Table 2: Part 2 Study Objective and Endpoints

Primary Objective	Primary Endpoints
To determine the safety and tolerability of DRF administered for up to 48 weeks in adult East Asian participants with RMS	
• Incidence of AEs and SAEs up to Week 48• Quantitative and qualitative changes from baseline (Visit 1) to Week 48 in clinical laboratory parameters, ECGs, and vital signs• Incidence of C-SSRS events at Baseline (Visit 1) and through Week 48

2.2. Study Design

This is a multicenter, open-label, single-arm, Phase 3 study to evaluate the safety and tolerability, and PK of DRF administered orally to East Asian participants with RMS.

Approximately 50 Japanese participants and 50 Chinese participants are planned to be enrolled.

This study will be conducted in 2 parts:

- Part 1 is designed to evaluate the PK, safety and tolerability of DRF administered orally.
- Part 2 is designed as a 24-week safety extension period for participants from Part 1.

During Part 1, participants will have up to 8 visits during the Treatment Period (i.e., Baseline Visit [Day 1], Week 2, Week 4, Week 8, Week 12, Week 16, Week 20, and Week 24) and will be contacted via telephone twice.

During Part 2, participants will report to the study site every 4 weeks up to Week 48 during the Treatment Period, for a total of 7 visits, and will have the Safety Follow-Up Visit 2 weeks later (Week 50) after the end of the Treatment Period.

Any participant who prematurely discontinues study treatment or withdraws from the study will be asked to return to the clinic to complete all study assessments for Week 48/ET Visit and for the Safety Follow-Up Visit 2 weeks later (Visit 15).

Participants who complete the study or who terminate the study early and have a last measured lymphocyte count < LLN will return to the clinic for additional LM visits every 2 months starting from Visit 15 (or from the ET visit for participants who terminate the study early) for a period of 6 months (i.e., a maximum of 3 visits), until lymphocyte counts reach normal limits (\geq LLN), or the participant commences therapy with another DMT, whichever occurs first (see, schedule of assessments in [Appendix A](#)).

Intensive blood samples will be collected pre-dose (-30 to 0 minutes pre-dose) and at various timepoints post-dose (0.5, 1, 2, 3, 4, 6 and 8-hours post-dose) at any timepoint in the period between Week 4 (Day 29, Visit 3 \pm 3 days) and Week 24 (Day 169, Visit 8 \pm 5 days), both inclusive for 7 Japanese participants who will take DRF after 10 hours of fasting, and no food will be allowed for at least 4 hours after the dose of DRF. Participants will be allowed water ad libitum, except for 1 hour before and 2 hours after administration of the dose of DRF. Sparse blood samples will be collected pre-dose (-30 to 0 minutes pre-dose) and 2 to 3 hours post-dose on Day 29 (Visit 3) and Day 57 (Visit 4) for all participants not included in the intensive PK cohort, as well as for those included in both the sparse and intensive PK cohorts if it is determined that intensive PK sampling is not feasible by Day 57. For those participants in the intensive PK cohort in which intensive PK sampling is completed on Day 29 or Day 57, sparse PK sampling will not be required for said days) (see, study design schematic in [Appendix B](#)).

2.3. Sample Size Considerations

A sample size of approximately 50 participants per cohort is based on feasibility considerations and is deemed sufficient to characterize the safety and tolerability profile. With this sample size, the probability of observing at least 1 SAE with a background incidence of 4% would be 87% based on data from the 24-week Treatment Period in Study ALK8700-A301 (a DRF global Phase 3 study) in RRMS participants who were naïve to DRF treatment.

In addition, assuming the incidence of GI AEs at 24 weeks of 27.5% as observed in participants naïve to DRF treatment recruited in Study ALK8700-A301, the sample size of approximately 50 participants per cohort will provide a 96% probability of observing a point

estimate of GI AE incidence rate < 39% in Part 1 of the study (at 24 weeks). The 24-week incidence rate of 39% was observed in East Asian participants who received DMF twice daily in Study 109MS305.

Based on the observed DRF PK parameters in fasted participants from ALK8700-A103 study, CV of AUC_{last} was estimated to be 30.9; therefore, a sample size of 7 Japanese participants would be needed to evaluate the MMF PK parameters with sufficient precision, which is defined as an evaluation of the PK parameters of MMF with at least 80% power to achieve a 95% CI within 60% to 140% of the geometric mean. Since the variability of HES parameters is significantly lower, the data from 7 participants will also provide a robust assessment of AUC_{last} and C_{max} of HES in Japanese MS participants.

The Sponsor may enroll fewer than 50 participants per cohort based on the observed recruitment rate in these regions.

3. Definitions

3.1. Dates and Points of Reference

- Study Day 1: the date of the first dose of study treatment
- Study relative day:
 - For a date on or after Study Day 1
$$\text{Study Day} = (\text{Date of Interest}) - (\text{Study Day 1}) + 1$$
 - For a date before Study Day 1
$$\text{Study Day} = (\text{Date of Interest}) - (\text{Study Day 1})$$
- Unless otherwise specified, baseline for assessments is defined as the last non-missing measurement taken on or prior to the first drug administration.
- Unscheduled visit measurements will not be included in the by visit summaries but will be included in the shift tables for safety parameters.
The determination of baseline values will be based on all measurements from both scheduled and unscheduled visits.
- No visit window analysis will be defined unless otherwise specified. Nominal visits/time points will be used for all statistical summaries.
- If a participant is terminated early from this study, he/she will be encouraged to complete the ET Visit at the time of study drug discontinuation and the Safety Follow-up Visit. In summary tables and statistical tests, all [REDACTED] and safety parameters measured at the ET Visit will be re-allocated according to the following rules:
 - If the ET Visit is closer to the previous scheduled visit for a given parameter and there is no measurement at that visit, the ET Visit will be re-allocated to the previous scheduled visit.
 - If the ET Visit is closer to the next scheduled visit for a given parameter and there is no measurement at that visit, the ET Visit will be re-allocated to the next scheduled visit.
 - Otherwise, the ET Visit will remain unassigned to a nominal visit.

The above re-allocation of the ET Visit will be performed for each █ and safety parameter based on its individual scheduled visits in the protocol.

3.2. Study Treatment

The study will consist of 2 treatment cohorts as follows:

- Cohort 1: approximately 50 Japanese participants with RMS
- Cohort 2: approximately 50 Chinese participants with RMS

Study treatment includes DRF 231 mg administered as 1 capsule twice daily and DRF 462 mg administered as two 231 mg capsules twice daily. Participants will titrate from DRF 231 mg twice daily for the first week on treatment to 462 mg twice daily from Day 8 onwards.

Starting on Day 8 of treatment, dose reduction to DRF 231 mg twice daily is permitted at the Investigator's discretion for participants who are unable to tolerate DRF 462 mg twice daily due to flushing or GI disturbances. Once a participant has stabilized after dose reduction, attempts should again be made to achieve and maintain the target maintenance dose of DRF 462 mg twice daily. If a participant remains unable to tolerate DRF 462 mg twice daily after 1 month on treatment, further dose reduction will not be permitted, and the participant will be discontinued from the study.

3.3. Study Periods

Study duration for participants who complete the study will be up to 54 weeks:

- 4-week Screening Period
- 24-week Treatment Period in Part 1
- 24-week Treatment Period in Part 2
- 2-week Safety Follow-Up Period

3.4. Key Derived Variables

- Study period in Part 1 is defined as the period from treatment start date to the latest study visit date for Week 24 or the study early termination visit date prior to Week 24 for discontinued subjects from study visit page.
- Study period in Part 2 is defined as the period from treatment start date to last study visit date from end of study page unless otherwise specified. This is a combined study period.
- Treatment period in Part 1 is defined as period from treatment start date to last exposure date on or prior to study scheduled day corresponding to Week 24 from either drug accountability or drug administration page whichever is the latest.
- Treatment period in Part 2 is defined as period from treatment start date to last exposure date from either drug accountability or drug administration page whichever is the latest. This is a combined treatment period.

3.5. Analysis Sets

Safety Analysis Set: defined as all participants who receive at least 1 dose of study treatment; this set will be used in the safety analyses.

PK Analysis Set: defined as all participants who receive at least 1 dose of study treatment and have had at least 1 post-dose plasma concentration for MMF and HES; this set will be used in the PK analysis with the following subsets of participants:

- with intensive PK Analysis Set
- with sparse PK Analysis Set

4. List of Planned Study Analyses

Statistical analyses will be performed using cleaned electronic clinical report form (eCRF) data collected. This SAP covers all planned analyses of the study.

4.1. Interim Analysis

The interim analysis of the Part 1 data will be performed after all the participants in the Japanese Cohort have completed the first 24-week Treatment Period (i.e., completed the Week 24 visit or discontinued the study before the Week 24 assessment). The analysis will evaluate the primary and secondary endpoints, [REDACTED] defined by Week 24 for Japan regulatory interaction.

The interim analysis of the combined data (Part 1 and Part 2) may be performed after all the participants in the Japanese Cohort have completed the first 48-week Treatment Period (i.e., completed the Week 48 visit or discontinued the study before the Week 48 assessment). The analysis will evaluate the primary and secondary endpoints, [REDACTED] defined by Week 48 for Japan regulatory interaction.

Additional interim analysis or post-hoc analysis may be performed to support regulatory interaction.

4.2. Final Analysis

The final analysis will be performed after all the participants in the Japanese and Chinese Cohorts have completed the 48-week Treatment Period along with 2-week Safety Follow-up Period or discontinued the study before the Week 48 assessment). In case, there is at least one participant who enters Lymphocyte Monitoring Period after 2-week Safety Follow-up Period, the final analysis will be performed upon having completed all required assessments for participant in Lymphocyte Monitoring Period. The analysis will evaluate the primary and secondary endpoints, [REDACTED] defined by End of the Study.

5. Statistical Methods for Planned Analyses

5.1. General Principles

5.1.1. Summary statistics

In general, descriptive summary statistics will be presented by cohort and overall for Part 1 data and combined data (Part 1 and Part 2). Categorical data will be generally summarized with counts and percentages of participants. The denominator used for the percentage calculation will be clearly defined. For all non-PK summaries, continuous variables will be summarized with the following descriptive statistics: n (number of observations), (arithmetic) mean, standard deviation, median, Q1, Q3, minimum and maximum. For PK summaries, variables will be summarized additionally with geometric mean and geometric CV%. Arithmetic CV% may also be provided. Two-sided 95% CIs will be presented for selected PK parameters and [REDACTED] as appropriate.

5.1.2. Adjustment for covariates

In [REDACTED], the choice of covariate(s) to be included in the model will be guided by prior knowledge of previous studies conducted in east Asian

population, as well as by an interest in expanding basic disease area knowledge. Selected covariates will be clearly presented in the statistical outputs and CSR.

5.1.3. Subgroup Variables

A subgroup analyses may be performed as a post-hoc analysis based on scientific feasibility and interest, as well as regulatory request.

5.1.4. Pooling Data of Study Centers

Data from study centers will be pooled for all analyses.

5.1.5. Handling of Missing Data

The missing data will not be imputed. All analyses will be performed based on the observed data, unless otherwise specified.

5.1.6. Handling of BLQ Values in PK Analysis

The full details for handling of BLQ values and missing concentration during NCA analysis are provided in Pharmacokinetic Analysis Plan (PKAP).

For all descriptive statistics and mean concentration plots, the measurements that are BLQ will be set to zero. The measurements that are BLQ will be set to missing for the semi-log plots. Missing concentrations at any sampling time point will not be imputed and therefore will remain not evaluable for the analysis of concentration data.

5.1.7. Handling Partial dates

Imputation of partial dates will be performed with standard methods based on the following guiding principles:

1. Imputed dates cannot exceed the participant's study end date.
2. Worst case-scenario (WCS) is considered when imputing dates. A participant having a treatment emergent adverse event or on-treatment intervention is considered WCS.
3. Partial dates will be imputed in a manner that maximizes duration of the event or intervention, but not to override guiding principles #1 and #2.

5.1.8. Scope of Data Impacted by Public Health Emergency

Due to the public health emergency (e.g., COVID-19), study data may impact. All efforts should be made to collect data impacted by public health emergency, including treatment and study discontinuation, protocol alternations, AEs, non-drug related therapies, concomitant medications.

5.1.9. Coding Conventions for Events and Medications

All adverse events, medical history and non-drug therapy will be coded with the Medical Dictionary for Regulatory Activities (MedDRA) using the version 26.1 or higher.

Concomitant medications will be coded using the World Health Organization – Drug Dictionary (WHO-DD) based on the version September 2023 or higher.

5.1.10. Analysis Software

Data processing, tabulation of descriptive statistics, parameter estimation, and graphical representations will be performed primarily using SAS (release 9.4 or higher) for Windows. If the use of other software is warranted, the final CSR will detail what software was used and for what purposes.

All non-compartmental analysis (NCA) will be performed using a validated software, Phoenix® WinNonlin® Version 8.3 or higher (Certara, USA).

5.2. Participant Accountability

The number and percentage of participants will be summarized by cohort and overall, for the following categories:

- Participants enrolled
- Screen failure
- [REDACTED]
- Safety analysis set
- PK analysis set (intensive and sparse)
- Participants completed the 24-week Treatment Period
- Participants discontinued the treatment during the 24-week Treatment Period and reasons for treatment discontinuation
- Participants withdrawn from study during the 24-week Treatment Period and reasons for study withdrawal
- Participants completed Overall Treatment Period based EOT form
- Participants discontinued the overall study treatment and reasons for treatment discontinuation
- Participants completed Overall study based on EOS form
- Participants withdrawn from the overall study and reasons for study withdrawal

Percentages for all categories of participants will be calculated using the number of participants dosed or Safety Analysis Set. Disposition data will also be presented in a listing.

In addition, data listings will be provided for screening, prior subject participation, and screening laboratory assessments.

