6.3. Screening, Retesting, and Screen Failures

6.3.1. Screening

Once informed consent is obtained, screening assessments can occur. At this time, a unique identification number is assigned that will be used on study-related documents pertaining to the participant. Any identification numbers that are assigned will not be reused, even if the participant does not receive treatment or continue in the study. Study sites are required to document all screened participants initially considered for inclusion in the study.

The screening period can be extended up to a maximum of 42 days (i.e., an additional 2 weeks) with prior approval of the medical monitor if the testing of teriflunomide levels or confirmation of accelerated elimination (per exclusion criterion 27e; Section 6.2) or minimum of 4 weeks' TB prophylaxis (per exclusion criterion 21c; Section 6.2) cannot be completed within the 28-day screening period.

CONFIDENTIAL

The information contained herein may not be used, disclosed, or published without the written consent of Biogen MA Inc.

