6.3.3. Screen Failures

Screen failures are defined as participants who sign the ICF but are not subsequently dosed. If a participant is considered a screen failure, the reasons for exclusion must be documented in the participant's source documents and on the screening log. A minimal set of screen failure information is required to ensure transparent reporting of screen failure participants to meet the Consolidated Standards of Reporting Trials publishing requirements and to respond to queries from regulatory authorities. Minimal information includes demography, screen failure details, eligibility criteria, and any SAEs.

All participants with incomplete enrollment due to a public health emergency (e.g., travel restrictions, participants who recovered after getting infected) will be eligible for rescreening provided that the participants met all eligibility criteria during the initial screening period, and that the reason for rescreening is incomplete enrollment due to a public health emergency. These participants will be reported as screen failed and then rescreened. Participants may have been provided with a unique identification number during Screening. The previously issued unique identification number will no longer be used, and a separate unique identification number will be provided during rescreening.

CONFIDENTIAL

The information contained herein may not be used, disclosed, or published without the written consent of
Biogen MA Inc.

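### SAP 5.2 divides screen failures by participants dosed, so the printed percentage is an odds and overstates the share of screened participants who failed

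*SAP*

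**What the plan says.** SAP 5.2 opens the disposition summary with "The number and percentage of participants will be summarized by cohort and overall, for the following categories". The list that follows includes participants enrolled and screen failure, then the analysis sets and the completion and discontinuation rows. After the list comes one rule for the denominator: "Percentages for all categories of participants will be calculated using the number of participants dosed or Safety Analysis Set". No exception is written for the rows that precede dosing. No row for participants screened is visible; one category is redacted, and its content is unknown.

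Two definitions decide what that rule does:

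- Protocol 6.3.3: "Screen failures are defined as participants who sign the ICF but are not subsequently dosed".
- SAP 3.5: "Safety Analysis Set: defined as all participants who receive at least 1 dose of study treatment".

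Protocol 6.3.3 adds a special case for enrolment left incomplete because of a public health emergency: "These participants will be reported as screen failed and then rescreened". These people receive a separate identification number, and the old one is retired. SAP 5.2 does not say whether its counts are of persons or of identification numbers. It also plans listings for screening and for prior participation, but attaches no percentage to them.

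**The concern.** A percentage beside a screen-failure count is normally read as the share of those screened who did not get in. The SAP's rule produces a different quantity: failures per 100 participants dosed. Under the two definitions a person who was screened once cannot be in both groups, so the result is a ratio of two separate groups and not a proportion of either.

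The stake is modest. Protocol 6.3.3 says that screen-failure information is kept for transparent reporting and publication. The exclusion list is long and removes people with GI disease, recent GI symptoms, or earlier Tecfidera discontinuation for tolerability (exclusion criteria 5, 6 and 27j). Some readers will use the share screened out to judge whom the tolerability results describe, and the table would give them a figure that is too high.

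**Working it through.** **Inputs**

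- F = screen failures: signed the ICF, not dosed (Protocol 6.3.3).
- D = participants with at least one dose, which is the Safety Analysis Set (SAP 3.5).
- Planned size, used as D for illustration: "Approximately 50 Japanese participants and 50 Chinese participants are planned to be enrolled" (SAP 2.2), so D is about 50 per cohort and 100 overall.
- Expected F: not given in either document. The values below are assumptions.

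The plan states no screen-failure figure, so there is none to reproduce.

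**Step 1. The two formulas.** Leaving rescreening aside, everyone who signed the ICF is either dosed or a screen failure, so the number screened is F + D.

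- Percentage under SAP 5.2: 100 × F/D
- Share of screened who failed: 100 × F/(F+D)

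**Step 2. The relation between them.** Put f = F/(F+D). Then 1 − f = D/(F+D), and F/D = f/(1−f), which is the odds of failing. It is larger than f for every f above zero.

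| Share of screened who failed, f | Printed under SAP 5.2, f/(1−f) |
|---|---|
| 10% | 0.10/0.90 = 11.1% |
| 20% | 0.20/0.80 = 25.0% |
| 30% | 0.30/0.70 = 42.9% |
| 40% | 0.40/0.60 = 66.7% |
| 50% | 0.50/0.50 = 100% |

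**Step 3. Counts for one cohort with D = 50.**

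| F | SAP 5.2: F/50 | Share of screened: F/(F+50) |
|---|---|---|
| 5 | 10.0% | 9.1% |
| 10 | 20.0% | 16.7% |
| 25 | 50.0% | 33.3% |
| 50 | 100.0% | 50.0% |
| 60 | 120.0% | 54.5% |

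The printed figure passes 100% only when F exceeds D: more than 50 failures in a cohort of 50, or more than 100 at 100 dosed overall.

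**Step 4. The enrolled row.** With E enrolled, the rule prints E/D. This is 100% if everyone enrolled is dosed, and above 100% if anyone is not.

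**Step 5. Rescreening after a public health emergency.** Suppose R people are reported as failed, rescreened once and then dosed. Counted by identification number, they sit in both F and D, and the share of screened numbers that failed is F/(F+D). Counted once per person by final status, the share is (F−R)/(F+D−R), which is lower whenever R is above zero. The SAP does not choose between the two.

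**The case against.** The best defence is that nothing is hidden. The SAP never calls this row a screen-failure rate; it declares the denominator openly, and SAP 5.1.1 commits to defining denominators clearly. The same table prints both F and D, so a reader can work out F/(F+D). Protocol 6.3.3 asks for screen-failure details and not for a percentage, no objective or endpoint uses the share screened out, and reasons for exclusion are recorded separately. All of this stands, and it keeps the point small. It does not make the denominator suitable: the rule is explicit, covers this row, and yields a figure that most readers would misread. Recovering the share from the counts also depends on knowing how rescreened people were counted.

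Two stronger readings are tempting, and the documents do not support either.

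- A reader might infer that the table will show a screen-failure figure above 100%. That needs more failures than dosed participants, and no expected number is given. It is possible but not shown to be likely.
- A reader might infer that every rescreened person gets a new number and stays counted as failed. Protocol 6.3.3 says so only for public health emergencies. Exclusion criteria 15, 16 and 22 allow rescreening after SARS-CoV-2 infection or contact, or another infection, and are silent on both matters. Protocol 6.3.1 says that assigned numbers are not reused, but not what a rescreened person receives.

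**Conclusion.** The point holds as a wrong denominator for one descriptive row, and for a second row if enrolment and dosing differ. Following SAP 5.2 as written overstates the share of screened participants who failed whenever there is at least one failure. That direction rests only on the two definitions. The size depends on an assumed failure share: the overstatement is about 1 percentage point at 10% (11.1 − 10), 5 at 20% (25.0 − 20) and about 13 at 30% (42.9 − 30).

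The counts are unaffected, subject to the open question on rescreened people. The dosed denominator suits the remaining rows. The primary safety endpoints, the PK analyses and the sample size do not change.

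**What to change.** In SAP 5.2:

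1. Use participants screened (signed ICF) as the denominator for screen failure and for participants enrolled.
2. Add a row for participants screened, unless the redacted category already is one.
3. Keep the dosed denominator for all remaining rows.
4. For people rescreened after a public health emergency, count each person once by final status where the two identification numbers can be linked. Otherwise count by number and footnote how many were rescreened.

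Items 1 to 3 cost a sentence and a table row. The number screened should already be on record, since Protocol 6.3.1 states: "Study sites are required to document all screened participants initially considered for inclusion in the study". Item 4 may cost a little more: the documents describe no variable that links an old number to a new one. The prior-participation listing planned in SAP 5.2 may serve, and the footnote is there in case it does not.
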